2.5.1.1 Adverse events of special interest / grouping of AEs

Adverse events of special interest will be summarized and also will be listed. AEs of special interest include the following, specified as compound-level risk factors defined in the Case Retrieval Strategy (CRS):

- Anaphylaxis (including Hypersensitivity reactions)
- Parasitic (Helminthic) Infection
- [REDACTED]
- Serum Sickness Syndrome/Serum Sickness Like Disease
- Neoplastic conditions
- Eosinophilic Conditions / Churg-Strauss Syndrome
- Arterial Thromboembolic Events (ATEs) / Cardiovascular toxicity
- Injection site reactions
- Thrombocytopenia
- Reduction in Vaccine Efficacy
- Liver Toxicity
- Contraceptive measures

2.5.1.2 Adjudication committee (AC)

Hypersensitivity assessment

All hypersensitivity reactions that are possible cases of anaphylaxis will be adjudicated by an independent committee. All adjudicated hypersensitivity reactions will be listed, and the treatment emergent adjudicated hypersensitivity reactions will be flagged.

Cardio- and Cerebrovascular events

All cardio- and cerebrovascular events will be adjudicated by an independent committee. All positively adjudicated events will be listed, and the treatment emergent adjudicated events will be flagged.

Malignancies

Adjudicated malignancies whether newly detected or worsening of existing malignancies will be listed, treatment emergent adjudicated events will be flagged.

Liver events and renal events

Liver events and renal events will be listed.

2.5.1.3 Deaths

Death while on study will be listed and reported by SOC and PT.

2.5.2 Laboratory data

The following hematology criteria will be assessed: Hemoglobin, hematocrit, red blood cell count, white blood cell count with differential, and platelet count. Also, coagulation will be assessed by International Normalized Ratio (INR).

The following biochemistry criteria will be assessed: Albumin, total bilirubin, alkaline phosphatase (ALP), aspartate aminotransferase (AST), alanine aminotransferase (ALT), chloride, calcium, sodium, potassium, magnesium, lactate dehydrogenase (LDH), creatinine, inorganic phosphorus, urea/BUN, uric acid and high sensitivity C-reactive protein (hs-CRP) will be measured.

The summary of laboratory evaluations will be presented for three groups of laboratory tests (hematology, serum chemistry and urinalysis). Descriptive summary statistics for the change from baseline to each study visit and maximum/minimum value will be presented for quantitative criteria. For qualitative criteria frequencies by categories at each visit will be summarized. These descriptive summaries will be presented by test group and laboratory test.

Change from baseline will only be summarized for subjects having both baseline and post baseline values. The maximum and minimum values could come from post-baseline scheduled, unscheduled or premature discontinuation visits. For laboratory test values below Lower Limit of Quantification (LLOQ) or above Upper Limit of Quantification (ULOQ) will be imputed as LLOQ or ULOQ value at the time of testing, respectively. The numerical part of the reported result will be treated as the actual LLOQ or ULOQ. These laboratory values will be displayed in listings using the standard unit with the reported sign i.e. “<” or “>”.

For hematology and serum chemistry, a shift table from baseline to the worst value during the treatment epoch will be presented based on normal range. The same shift table will be done with the worst value during the post-treatment follow-up epoch.

The notable criteria for platelet count ($<75,000\mu\text{L}$), for serum creatinine ($\geq 50\%$ increase compared to baseline), for AST, ALT or INR above 1.5x Upper Limit of Normal (ULN), for creatinine above ULN and stool test result positive for ova or parasites, will be used to calculate number and percentage of patients with newly occurring or worsening notable abnormalities occurring during the treatment epoch and also occurring during the post-treatment follow-up epoch. A case will be considered as newly occurring if the value for a laboratory evaluation is not notable or missing at baseline but is notable thereafter; a case will be considered as worsening if the value for a laboratory evaluation is notable at baseline and at least one post-baseline value is worse than baseline.

To evaluate potential drug-induced liver injury, newly occurring liver enzyme abnormalities at any time post-baseline will also be summarized for treatment epoch and for post-treatment follow-up epoch based on the event criteria given below defined in the protocol [\[Section 13.2\]](#).

Table 1-5 Liver-related events

Parameter	Notable criterion
ALT	$>3\text{xULN}$; $>5\text{xULN}$; $>8\text{xULN}$; $>10\text{xULN}$; $>20\text{xULN}$
ALT or AST	$>3\text{xULN}$; $>5\text{xULN}$; $>8\text{xULN}$; $>10\text{xULN}$; $>20\text{xULN}$
(ALT or AST) & TBL	$>3\text{xULN}$ & (TBL $>1.5\text{xULN}$; $>2\text{xULN}$)
(ALT or AST) & INR	$>3\text{xULN}$ & INR >1.5

Parameter	Notable criterion
TBL	>1xULN; >1.5xULN; >2xULN
ALP	>1.5xULN, >2xULN; >5xULN
ALP & TBL	>3xULN; >5xULN & TBL>2xULN
(ALT or AST) & TBL & ALP	ALT or AST>3xULN & TBL>2xULN & ALP≤2xULN (potential Hy's Law case)
(ALT or AST) and (nausea or vomiting or fatigue or general malaise or abdominal pain or (rash and eosinophilia))	> 3 x ULN and (nausea or vomiting or fatigue or general malaise or abdominal pain or (rash and eosinophilia))

AST = Aspartate aminotransferase; also known as SGOT, ALT = Alanine aminotransferase; also known as SGPT, INR=International Normalized Ratio, ALP = Alkaline phosphatase, TBL = Total bilirubin

For potential Hy's Law case, all the elevations must occur at the same post-baseline time point. A case will be considered as newly occurring if a criterion is not met or missing at baseline but is met thereafter. Laboratory data will be listed by patient and time point and values outside the normal ranges or satisfying the notable criterion will be flagged.

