11. Onset of clinically significant cardiovascular (such as but not limited to myocardial infarction, unstable ischemic heart disease, NYHA Class III/IV left ventricular failure arrhythmia, uncontrolled hypertension within 12 months prior to visit 206), neurological, psychiatric, metabolic, or other pathological conditions such as but not limited to cerebrovascular disease, neurodegenerative diseases, or other neurological disease, uncontrolled hypo- and hyperthyroidism and other autoimmune diseases, hypokalemia, hyperadrenergic state, or ophthalmologic disorder that could interfere with the compromise the safety of the patients, interfere with evaluation or interpretation of the study results, or preclude completion of the study
12. Medical examination or laboratory findings that suggest the possibility of decompensation of co-existing conditions for the duration of this study. Any items that are cause for uncertainty will be reviewed with the investigator
13. History or current treatment for hepatic disease including but not limited to acute or chronic hepatitis, cirrhosis or hepatic failure or AST/ALT levels or INR of more than 1.5x upper limit of normal (ULN)
14. History of renal disease or creatinine level above 1.5x ULN at visit 206
15. Platelets < 100,000/ μ L at visit 206
16. Long QT syndrome or whose QTcF (Fridericia) measured at end of core study visit (Visit 206) is prolonged (> 450 ms for males or > 460 ms for females) and confirmed by a central assessor (ECG measurement should not be repeated in these patients to confirm eligibility)
17. Pregnant or nursing (lactating) women, where pregnancy is defined as the state of a female after conception and until the termination of gestation, confirmed by a positive hCG laboratory test
18. Women of child-bearing potential, defined as all women physiologically capable of becoming pregnant, unless they are using effective methods of contraception during dosing of study treatment. Effective contraception methods include:
 - Total abstinence (when this is in line with the preferred and usual lifestyle of the subject. Periodic abstinence (e.g., calendar, ovulation, symptothermal, post-ovulation methods) and withdrawal are not acceptable methods of contraception

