9.4.2 Statistical model, hypothesis, and method of analysis

No hypotheses will be tested.

Adverse events will be summarized by presenting the number and percentage of patients having any AE by primary system organ class and/or preferred term. AE by severity, drug related AEs, AEs leading to premature discontinuation of study drug, death and serious AEs will be presented in a similar format as all AEs.

AEs related to potential anaphylaxis will be summarized separately.

Laboratory and vital sign data will be summarized by presenting summary statistics of values and change from baseline by visit, and by presenting frequency of patients with clinically notable changes.

[figure not shown]
ECG intervals will be summarized by presenting summary statistics for change from baseline values by visit. Count and frequency of clinically notable ECG abnormalities or changes will be presented. The (uncorrected) QT interval will be corrected according to the Fridericia's formulae.

Laboratory data, vital sign data and ECG data will be listed with abnormal value flagged based on normal ranges or clinically notable ranges.

Other safety data will be summarized and listed as appropriate.

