9.7 Sample size calculation

It is expected that approximately 240 patients will enter the extension study. The following graph shows the binomial probability of observing at least one event for a range of true incidences from 0.001 (0.1%) to 0.05 (5%) in samples of 200, 250 and 300 patients.

Figure 9-1 Probability of observing adverse events with given incidence

10 Ethical considerations

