2.1.4 Baseline definitions

Core study baseline definition-

Core study baseline is the last assessment (including unscheduled visits) obtained before the first dose of core study treatment.

For the following demographic information - sex, race, ethnicity and height and baseline characteristics, randomization/background medication strata and positive chronic urticaria group, core study baseline information will be used.

Extension study baseline definition –

For eDiary weekly score, the E1 baseline is the score derived from E1 study day -7 to E1 study day -1.

If the questionnaire was completed more than once on the same date, on the last date on or before treatment start date, then the worst outcome (i.e. the highest score) of the duplicate observations on that date will be used for baseline.

For the safety analysis, the baseline will be the last assessment prior to or on the first study dose and on or after visit 206, unless otherwise specified. Note: if time is collected (i.e. hematology chemistry and ECG) the last assessment prior to or on the same time as first study dose will be used. If time is not collected then, the assessment is assumed to be prior if it's on the same date as first study dose.

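### SAP 2.5.2 counts a laboratory abnormality that arose on treatment as newly occurring again in follow-up; a narrower fault is that any single value beyond a notable baseline counts as worsening

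*SAP*

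**What the plan says.** SAP 2.5.2 asks for the number and percentage of patients with "newly occurring or worsening notable abnormalities occurring during the treatment epoch and also occurring during the post-treatment follow-up epoch". The criteria are platelets below 75,000, a creatinine rise of at least 50% from baseline, and limits "for AST, ALT or INR above 1.5x Upper Limit of Normal (ULN), for creatinine above ULN and stool test result positive for ova or parasites".

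A case is newly occurring if it is "not notable or missing at baseline but is notable thereafter". It is worsening if it is "notable at baseline and at least one post-baseline value is worse than baseline". Neither definition has a minimum change or a confirmation step.

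Table 1-5 (liver-related events) is also reported for each epoch and uses the same newly-occurring definition. It has no worsening category.

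Only one baseline serves both epochs. SAP 2.1.4 says that "the baseline will be the last assessment prior to or on the first study dose", provided it is on or after Visit 206; in practice this is usually the Visit 301 sample. Protocol 9.4.1 instead sets the safety baseline at Visit 206, except for parameters first assessed at Visit 301.

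Exclusion criterion 14 (Protocol 4.2) bars a "creatinine level above 1.5x ULN at visit 206". Protocol Appendix 1 lists creatinine above ULN among its limits and says that patients above those limits at Visit 206 should be excluded.

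**The concern.** Laboratory changes are part of the primary objective, and the study has a single arm, so no control group shows how many cases a counting rule produces by itself. The rule has two weaknesses.

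- **Recounting.** Protocol 3.2 gives follow-up the task of assessing safety after treatment stops. A follow-up row that mixes abnormalities arising after the last dose with abnormalities that have not resolved cannot do this. The two situations have different safety meanings, and the recount reaches the liver table, including potential Hy's Law cases.
- **Chance worsening.** A patient who starts above a limit is compared with one baseline value at up to 12 later treatment visits. One small upward fluctuation is enough to be counted.

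**Working it through.** The plan gives no figure for this rule, so there is nothing to reproduce.

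**Inputs from the documents.** About 240 patients (Protocol 9.7). Laboratory samples at Visits 302-313, so 12 post-baseline samples on treatment, and at Visits 401-405, so 5 in follow-up (Protocol Table 6-1, which places Visit 401 in follow-up). The last dose is at Visit 313, Day 337, and Visit 401 is Day 365. The first follow-up sample is therefore 365 - 337 = 28 days after the last dose.

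**Step 1: recounting, from the text alone.** Take two patients whose ALT is not notable at the extension baseline.

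| | Treatment epoch | Follow-up epoch | Treatment count | Follow-up count |
|---|---|---|---|---|
| Patient A | notable at 312 and 313 | still notable at 401, then normal | newly occurring | newly occurring |
| Patient B | never notable | first notable at 403 | none | newly occurring |

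The follow-up row treats A and B alike. No text in the SAP removes A from it.

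**Step 2: how much recounting.** Model: value = patient effect + independent visit error, normal, with no change over time. Assumptions not in the documents: within-patient correlation ρ of 0.5 to 0.95, and 2.5% to 5% of single samples notable. Of the follow-up newly-occurring patients, 59% (ρ = 0.5, 2.5%) to 83% (ρ = 0.95, 5%) had already been notable on treatment. A rule that looks only at the last treatment value would remove about 12-30% of the follow-up cases. A rule that looks at every treatment-epoch value removes the full 59-83%.

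**Step 3: which criteria the worsening rule can reach.**

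| Criterion | Can it be notable at baseline and then worsen? |
|---|---|
| Platelets < 75,000 | Hardly: values below 100,000 at Visit 206 are excluded |
| AST, ALT, INR > 1.5x ULN | Only if the value crosses the limit between Visits 206 and 301, as entry and notable limits coincide |
| Creatinine rise ≥ 50% | No: it is defined relative to baseline |
| Stool positive | No: positive or negative only |
| Creatinine > ULN | Yes under criterion 14; under Appendix 1 only by crossing between Visits 206 and 301 |

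**Step 4: chance of a false worsening.** If the baseline and k later values were exchangeable, P(at least one worse) = k/(k+1), which is 12/13 = 92% on treatment and 5/6 = 83% in follow-up. The rule applies only to patients whose baseline is already extreme, however, and their later values tend to fall back. The same model, restricted to patients notable at baseline, gives:

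| Single-sample prevalence, ρ | No entry screen: treatment / follow-up | Visit 206 within limit: share notable at baseline | Visit 206 within limit: treatment / follow-up |
|---|---|---|---|
| 2.5%, 0.5 | 48.6% / 30.6% | 2.1% | 43.6% / 26.4% |
| 2.5%, 0.95 | 83.9% / 70.7% | 0.76% | 69.6% / 52.5% |
| 5%, 0.5 | 56.8% / 37.8% | 3.95% | 50.9% / 32.2% |
| 5%, 0.95 | 85.1% / 72.3% | 1.36% | 71.1% / 52.6% |

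Expected false treatment-epoch cases per parameter = 240 × share notable at baseline × probability:

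- No entry screen: 240 × 0.025 × 0.486 = 2.9 to 240 × 0.05 × 0.851 = 10.2.
- Visit 206 within the limit: 240 × 0.0076 × 0.696 = 1.3 to 240 × 0.0395 × 0.509 = 4.8.

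**Step 5: effect of a 25% step for creatinine.** With 2.5% prevalence, ρ of 0.7 to 0.9 and no entry screen, the treatment-epoch probability falls from 63-79% to 0.01-0.1% if the within-patient CV is 5%, to 4-11% if it is 10%, and to 13-29% if it is 15% (assumed CVs).

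**The case against.** New since the extension baseline is a coherent definition. The study is descriptive ("No hypotheses will be tested"), so no error rate or power is affected. Listings by patient and time point will flag notable values, so onset and persistence can be traced for each patient, and a sizeable creatinine rise has its own criterion of at least 50%. All of this stands. It does not make the follow-up count interpretable: the SAP shift tables also run from the pre-dose baseline to the worst value in each epoch, so they carry the same ambiguity, and only the listings separate the two situations. If new since extension baseline is what is meant, the SAP should say so. Scheduled stool tests are outside the recount, because samples are planned only at Visits 206 and 401.

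On worsening, a reader might infer that a false count is nearly certain for anyone notable at baseline, citing 12/13. That figure ignores regression to the mean and lies above every conditional result in Step 4. A reader might also infer that patients with creatinine between ULN and 1.5x ULN are certainly enrolled. The documents do not settle this: criterion 14 admits them and Appendix 1 excludes them. With the Appendix 1 limit and the Visit 206 baseline of Protocol 9.4.1 together, almost no one would be notable at baseline.

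**Conclusion.** The recount holds on the wording alone and needs no assumption. It applies to every criterion with repeated samples and to Table 1-5. Its share of the follow-up count, 59-83%, depends on the no-change model and the assumed correlation and prevalence.

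The worsening fault is real but secondary. With no drug effect, an affected patient is counted with a probability of roughly 45-85% on treatment and 25-70% in follow-up, about 1-10 of 240 patients per parameter in the treatment epoch. It acts mainly on creatinine above ULN and on values that cross a limit between Visit 206 and the Visit 301 baseline. The documents do not support the view that the whole laboratory table is inflated. The trial is not invalidated, but a primary safety count would mislead and should be corrected.

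**What to change.** 1. **Follow-up epoch, including Table 1-5.** Count a case as newly occurring only if the criterion was met neither at baseline nor at any treatment-epoch value. Show cases notable during treatment and again or still notable in follow-up in their own row. Testing only the last treatment value is not enough (Step 2).
2. **Worsening.** Report it in a separate row from newly occurring. For creatinine above ULN, count worsening only at a rise of at least 25% over baseline. Protocol Table 7-1 already uses that size; here it serves as a counting rule only. A step based on Table 1-5 categories should not be used: the lowest ALT category is above 3x ULN, so a rise from 1.6x to 2.9x ULN would be lost. TBL and ALP need no step, because the worsening rule does not cover them.
3. **Reconcile** the creatinine limits in exclusion criterion 14 and Appendix 1, and the safety baselines in Protocol 9.4.1 and SAP 2.1.4. The number of patients at risk of a false worsening depends on both.

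Items 1 and 2 need SAP wording and slightly more programming, and no new data. The downside is that creatinine worsenings below 25% would appear only in the listings and the by-visit change summaries.

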2.5.3 Vital signs

Vital signs (i.e. blood pressure and pulse rate) will be summarized by presenting summary statistics of values and change from baseline by visit. Change from baseline will only be summarized for patients having both baseline and post-baseline values. In addition, frequency of patients with clinically notable values will be presented for both the treatment and follow-up epochs. Patients with notable vital signs as defined below will also be listed.

A notable value is defined as follows:

- Pulse rate below 60 bpm (bradycardia)
- Pulse rate above 100 bpm (tachycardia)
- Systolic blood pressure (SBP) greater than or equal to 140 mmHg
- SBP lower than 90 mmHg
- Diastolic blood pressure (DBP) greater than or equal to 90 mmHg
- DBP lower than 60 mmHg.

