The following analyses will be performed, where appropriate, for measurements of urinalysis, hematology and blood chemistry tests:

Standard descriptive statistics for values measured at baseline and post-baseline visits including changes from baseline, shift tables relative to the normal ranges between baseline and post-baseline visits, number (and percentage) of patients with clinically notable changes for selected tests.

[REDACTED]

[REDACTED]

[REDACTED]

Vital signs

Vital signs (i.e. blood pressure, pulse rate and) will be summarized with standard descriptive statistics of raw data and changes from baseline for each visit separately. The numbers of patients with vital signs meeting the definition of notably abnormal will be presented by parameter.

ECG

ECG data will be summarized by treatment and visit. Changes from baseline will be summarized.

Notable QTc values and change from baseline will be summarized. A notable value is defined as a QTc interval of greater than 450 ms. The categories used for the change (increase) in QTc are - less than 30 ms, 30 to 60 ms and greater than 60 ms.

The Fredricia QT correction formula (QTcF) will be used for clinical decisions.

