2.5.4 ECG

ECG intervals will be summarized by presenting summary statistics for values and change from baseline values by visit. ECGs are planned to be performed in triplicate (other than baseline ECG results, which has been collected once), therefore the mean of the patients' scheduled measurements, by visit, will be used in the summary statistics.

Count and frequency of clinically notable ECG abnormalities or changes will be presented for patients with newly occurring or worsening notable abnormalities occurring post-baseline. For

ECGs, a notable corrected QT Interval (QTc) value is defined as a QTcF (Fridericia's) interval of greater than 450 msec for males and greater than 460 msec for females. The categories used for the change (increase) in QTcF are - greater than 30 msec and greater than 60 msec.

ECG evaluation for all subjects with at least one visit, with the most common interpretation of that visit is abnormal, will be listed. ECG interval data will be listed for all patients and abnormal value flagged based on clinically notable ranges.

A shift table from baseline to the worst post-baseline value will be presented based on the overall ECG interpretation.

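### The notable vital-signs counts in SAP 2.5.3 mix pre-existing with new findings, and their two epoch percentages are not comparable

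*SAP*

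**What the plan says.** Three neighbouring SAP sections count notable values under different rules.

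- **Vital signs (SAP 2.5.3):** "frequency of patients with clinically notable values will be presented for both the treatment and follow-up epochs". No baseline condition, shift table or split by baseline status is given. The section also plans values and change from baseline by visit, and a listing of patients with notable values.
- **Laboratory (SAP 2.5.2):** "number and percentage of patients with newly occurring or worsening notable abnormalities", by epoch. Worsening means "notable at baseline and at least one post-baseline value is worse than baseline". For hematology and chemistry, shift tables from baseline to worst value are planned for each epoch.
- **ECG (SAP 2.5.4):** "patients with newly occurring or worsening notable abnormalities occurring post-baseline", plus a shift table on the overall interpretation.

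The protocol is mixed. Section 9.4.1 asks for a plain count: "The numbers of patients with vital signs meeting the definition of notably abnormal will be presented by parameter". Section 9.4.2, treating laboratory and vital-sign data together, asks for the frequency of patients with notable changes. The readable part of SAP section 4 does not address the vital-sign rule; some of its bullets are redacted.

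**The concern.** Changes in vital signs are part of the primary objective (Protocol 2.1, SAP 1.2.1). The study has one arm, so each patient's own baseline is the main reference. SAP 2.1.4 defines that baseline, so the data exist.

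Exclusion criterion 11 (Protocol 4.2) covers onset of uncontrolled hypertension but sets no limit for blood pressure or pulse. A patient can therefore enter with a systolic value already at or above the SAP's limit ("Systolic blood pressure (SBP) greater than or equal to 140 mmHg"), stay there, and appear in the treatment-epoch count. The table would not tell that patient from one who became notable on QGE031.

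A second feature affects the same table. A patient counts if notable at any visit in the epoch, and the epochs differ in length. Table 6-1 schedules vital signs at every visit: 12 post-baseline treatment visits (302 to 313) and 5 follow-up visits (401 to 405). More visits give more chances to cross a limit. A reader who sees a higher percentage on treatment than in follow-up could take it for a drug effect.

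**Working it through.** The documents give no expected figure for notable vital signs, so there is nothing to reproduce. The size is illustrated with assumed distributions and no drug effect.

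**Inputs**
- From the documents: systolic limit 140 mmHg (SAP 2.5.3); 12 treatment and 5 follow-up visits (Protocol Table 6-1); about 240 patients (Protocol 9.7).
- Assumed: systolic mean 125, between-patient SD 12, visit-to-visit SD 8 (varied 6 to 10); a lower case with mean 120 and SDs 10 and 5. For pulse: mean 74, SDs 9 and 6.

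**Model.** Patient i has a true level m_i ~ N(mean, SD_between²). Each reading, including baseline, is m_i plus independent N(0, SD_visit²) error. The chance of being notable at least once in K visits is 1 − E[Φ((140 − m_i)/SD_visit)^K], evaluated by simulation.

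**Step 1: any single visit, including baseline.** z = (140 − 125)/√(12² + 8²) = 15/14.42 = 1.04, so about 14.9% are notable. This is the same at every visit, on or off drug.

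**Step 2: ever notable in the epoch.**

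| Assumed case | 12 visits | 5 visits |
|---|---|---|
| Systolic ≥140, mean 125, SDs 12 and 8 | 44% (about 106 of 240) | 33% (about 79 of 240) |
| Systolic ≥140, mean 120, SDs 10 and 5 | 13% (about 31 of 240) | 9% |
| Pulse <60, mean 74, SDs 9 and 6 | 33% | 24% |

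With the first case and visit SDs of 6, 8 and 10, the 12-visit figure is about 33%, 44% and 54%. If Visit 401 (Week 52) is assigned to treatment, the split is 13 against 4 visits and the first row becomes about 45% against 31%.

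**Step 3: how much of the count is pre-existing.** In the first case about 94% of patients notable at baseline are notable again on treatment: 14.9% × 0.94 = 14.0% of all patients, or 14.0/44 = 32% of those counted. Over visit SDs of 6 to 10 this share runs from about 37% down to 29%. The rest were not notable at baseline: about 35% of such patients cross the limit at least once in 12 visits by chance, and 24% in 5 visits. Thus 0.35 × 85.1% = 29.8%, and 29.8% + 14.0% = 44%.

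**Step 4: what the laboratory rule would give.** Newly occurring contributes 29.8%. Worsening, met by any one reading worse than baseline, catches about 77% of those notable at baseline: 14.9% × 0.77 = 11.5%. The total is 41.3%, against 44% under SAP 2.5.3. With visit SD 6 it is 32% against 34%; for pulse, 31% against 33%. The wording differs, but the count hardly moves.

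**Step 5: dependence on the notable limits.**

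| | Protocol Appendix 1 | SAP 2.5.3 |
|---|---|---|
| Low pulse | <40 | <60 |
| High pulse | >90 | >100 |
| High systolic | >140 | ≥140 |
| Low diastolic | <65 | <60 |
| High diastolic | >90 | ≥90 |

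In the pulse model above, a limit of 40 gives about 0.6% instead of 33%. The systolic illustration is essentially the same under either document.

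**The case against.** The strongest reply is that baseline is already used. SAP 2.5.3 summarises change from baseline by visit, which is free of the ever-count effect, and lists every patient with a notable value. The plan is descriptive, and Protocol 9.4.1 asks for just this plain count. All of that stands. It does not meet the narrower point: group means cannot show which patients are newly notable, and a listing leaves the reader to rebuild the split.

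Some stronger readings are tempting, and the documents do not support them.

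- *The SAP instructs that baseline be ignored.* It is silent, and table shells not seen here could add a condition. Since SAP 2.5.2 and 2.5.4 state theirs, the silence reads as a different rule, but it is silence.
- *The laboratory and ECG rule would cure the problem.* Step 4 shows that it would not.
- *Most counted patients would be pre-existing cases.* Under the assumptions used, roughly two thirds were not notable at baseline; most of the excess comes from counting over many visits.
- *A planned treatment-versus-follow-up comparison is biased.* No such comparison is planned. The two percentages are merely presented and invite one.
- *The unequal number of visits is peculiar to vital signs.* The laboratory counts in SAP 2.5.2 use the same epochs and blood-sampling visits, so they share it.
- *A naturally slow pulse will be reported as an on-treatment finding.* This holds only under the SAP's limit of 60, not the protocol's limit of 40.

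The sizes are also open to challenge. No mean or SD is in the documents, blood pressure is the mean of three readings (Protocol 6.5.2), which reduces noise, and the hypertension exclusion may lower the baseline rate.

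**Conclusion.** The concern holds as a minor weakness of presentation in a primary-objective table. As written, SAP 2.5.3 does not separate new from pre-existing notable vital signs, departs from the baseline-conditioned laboratory and ECG counts, and does not deliver the notable changes named in Protocol 9.4.2, though it agrees with 9.4.1. The textual finding needs no assumptions beyond reading the section at face value.

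The size does rest on assumptions. With no drug effect, the treatment-epoch systolic count could plausibly lie anywhere from about 13% to 54%; in the central case it is 44%, against 33% in follow-up. These figures show direction and mechanism; they are not forecasts for this population.

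**What to change.** In SAP 2.5.3, for each parameter and epoch, add one of these:

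- a shift table from baseline category to worst value; or
- the number newly notable among patients not notable at extension baseline, with that number as denominator, plus a separate row for patients notable at baseline. That row should show worsening by a prespecified minimum change, so that a real rise from a high baseline is not hidden and a single slightly worse reading does not qualify.

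Also add the frequency of notable values at each visit, baseline included. This is the display that removes the 12-against-5 imbalance; conditioning on baseline alone leaves it (35% against 24% in Step 3). Do not simply import the laboratory wording.

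Reconcile the notable limits in Protocol Appendix 1 with those in SAP 2.5.3, and record the outcome in SAP section 4 together with the counting rule.

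The cost is one extra table and a few lines of SAP text. No new data are needed.
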